12.1 Disposition of Subjects and Discontinuations

Summaries of the number and percent of subjects to enter, complete or discontinue study and treatment will be presented.

The number and percent of subjects for the following will be presented by original randomized treatment arm and overall:

- Number of subjects screened
- Number of subjects not randomized, and by reason
- Number of subjects randomized
- Number of subjects who have not received treatment after being randomized
- Number of subjects who completed or prematurely discontinued treatment, and by reason
- Number of subjects who prematurely discontinued the study after randomization, and by reason
- Number of subjects included in the PK sub-trial and the number who discontinued from the PK sub-trial.

Further summaries will also present the number of subjects in each of the analysis sets overall and by site. A summary and a listing of the reasons for exclusion from the PP analysis set will also be presented.

The results of the randomization algorithm according to IWRS will be summarized as follows:

- Number of randomized subjects overall, by country
- Number of randomized subjects by the previous systemic therapy use (non-biological or biologic naïve subjects versus biological or biologic experienced subjects) randomization strata (IWRS).

12.2 Demographics

Age at informed consent, sex, race and ethnicity will be summarized by treatment arm and overall for the ITT and the PP analysis sets. No formal comparison will be made between the treatment arms.

Age (years) at informed consent will be calculated as:

(Date of informed consent - date of birth + 1)/ 365.25

Specifications for computation of partial dates:

- In case of missing day only: Age [years]: (year/month of given informed consent year/month of birth)
- In case only year of birth is given: Age [years]: (year of given informed consent year of birth).

12.3 Medical History

Medical history data will be summarized by system organ class (SOC) and preferred term (PT) by treatment arm and overall for the ITT and PP analysis sets. Medical history terms will be coded using version 19.1 (or later) of the Medical Dictionary for Regulatory Activities (MedDRA). Listings of medical history will be sorted by treatment arm, subject identifier, start date of medical history event, SOC, PT and end date of medical history event.

12.4 Other Baseline Characteristics

History of rheumatoid arthritis (time (in months) since diagnosis relative to informed consent) will be summarized by treatment arm and overall for the ITT and PP analysis sets. Baseline assessments for the ACR component variables (tender joint count (TJC), swollen joint count (SJC), Patient's and Physician's Global Assessment of Disease Activity, Patient's Assessment of Arthritis Pain, Patient's Assessment of Physical Function as measured by the HAQ-DI and CRP), DAS28-ESR, CDAI, SDAI and tuberculosis assessment at baseline will also be summarized by treatment arm and overall for the ITT and PP analysis sets.

Methotrexate dose at baseline will be summarized by treatment arm and overall for the ITT and PP analysis sets.

Height (cm), weight (kg), BMI (kg/m²), vital signs (body temperature, heart rate, respiration rate and blood pressure), and ECG interpretation at baseline will be summarized by treatment arm for the ITT and PP analysis sets.

Height will be presented in centimeters (cm) and weight will be presented in kilograms (kg). The conversion factors used will be:

- Height in cm = Height in inches $\times 2.54$
- Weight in kg = Weight in pounds / 2.2046

ADA status, ADA titer and NAbs status at baseline will be summarized by treatment arm for the ITT and the PP analysis sets.

13 Previous or Concomitant Medications/Procedures

Medications which are taken by subjects other than study medications (MSB11022 or Humira) will be defined as previous or concomitant medication.

Previous medications will be defined as those that started and stopped before the first dose of study medication.

Concomitant medications will be defined as those that started before or during the treatment period (and up to the 4 week Safety Follow-up visit or 28 days after the last dose of study drug, whichever comes later) and finished during the treatment period or are ongoing.

In case the date values will not allow to unequivocally allocate a medication as previous or concomitant, the medication will be considered as a concomitant medication.

Previous and concomitant medications will be summarized by Anatomical Therapeutic Chemical (ATC) Level 2 and PT. Medications will be coded by the Enhanced World Health Organization Drug (WHODrug) dictionary, version September 2016 or later. In case multiple ATC's are assigned to a drug, all ATC-2nd level will be used for reporting.

Procedures will also be classed as concomitant using the same criteria defined above. Procedures will not be coded but the number of procedures overall and the name of procedure and reason for procedure will be summarized for each treatment arm.

14 Treatment Compliance and Exposure

Compliance and exposure data will be summarized by treatment arm. The following will be derived:

• Treatment duration (in weeks): calculated as the number of weeks from the first dose to the last dose in the study. Treatment duration (weeks) is defined as:

duration =
$$\left(\frac{\text{date of last dose - date of first dose} + y}{7 \text{ days}}\right)$$

where

y = 7 for subjects whose last dose was the Week 0 dose

y = 14 otherwise

• Total number of injections administered: Any administration of study medication regardless of the actual dose (any dose > 0 mg) will be counted as one injection. These data will come from the eCRF.

• Compliance will be estimated as the proportion of the planned number of injections actually administered. Compliance will be summarized as a continuous variable, as well as the number and percent of subjects with $\leq 80\%$, $> 80 - \leq 100\%$, $> 100\% - \leq 120\%$ and > 120% compliance.

Compliance (%) = 100 * (total number of injections received/ number of planned injections). For subjects who withdraw from study treatment prematurely, the number of planned injections will be the number planned up to the point of withdrawal.

15 Endpoint Evaluation

The subsections in this section include specifications for analyzing clinical trial endpoints specified in the CTP to meet the trial objectives.

15.1 Primary Endpoint Analyses

The primary endpoint is the occurrence of treatment-emergent AESIs (hypersensitivity) up to Week 52.

The primary analysis will be based on the safety analysis set.

The following is considered pre-defined AESI for this trial:

Hypersensitivity (defined by Standardized MedDRA Queries [SMQs] narrow as per the latest MedDRA version).

The proportions of subjects with AESIs (hypersensitivity) and accompanying 95% CIs (Exact 95% CIs, calculated with the Clopper-Pearson method) will be provided for each treatment arm. Half width of 95% CIs for the difference between treatment arms in occurrence for the most commonly observed clinical events of AESI (hypersensitivity) will also be presented. The cut-off point for the selection of the most commonly observed clinical events will be decided prior to the database lock and the treatment unblinding.

Listings of all AESIs (hypersensitivity) and listings of AESIs (hypersensitivity) with NCI-CTCAE Grade \geq 3 will be provided.

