## 4 Trial Objectives

### 4.1 Primary Objective

The primary objective of this study is to evaluate the safety profile of MSB11022-CCI compared to Humira® in patients with moderately to severely active RA up to Week 52.

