## 5.2.3 Rationale for Endpoints

### 5.2.3.1 Primary Endpoint

#### Incidence of AESI (Hypersensitivity) including and up to Week 52

In order to provide long-term safety and immunogenicity data in patients to support the new CCI formulation, this descriptive study will evaluate the safety and immunogenicity profile of MSB11022-CCI compared to the Humira® in patients with moderately to severely active RA who have had an inadequate response to MTX. In such a population, the rate of most commonly observed hypersensitivity events is 26.5% for the injection site reactions and 11% for rash (29).

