## 8.5 Description of Statistical Analyses

### 8.5.1 General Considerations

Full details of all planned analyses will be provided in the SAP, to be finalized and approved prior to database lock.

Baseline is defined as the day on which the first dose of the IMP (blinded trial drug) is administered.

Descriptive statistics will be given with reference to the analysis set deemed appropriate for each particular endpoint.

The following descriptive statistics will be used to summarize the trial data per treatment group on the basis of their nature unless otherwise specified:

- Continuous variables: n (number of non-missing observations), mean, standard deviation, 95% confidence interval (CI), median, minimum, and maximum
- Categorical variables: Frequencies and percentages
- Time to event variables: Kaplan-Meier estimates and 95% CIs

No correction for multiplicity is anticipated.

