### 8.5.2 Analysis of Primary Endpoint

The primary safety (safety population) endpoint will be summarized by treatment group using the Safety analysis set. Incidence of AESIs and 95% CIs will be provided for each treatment group. Half width of 95% CIs for the difference in incidence for the most commonly observed clinical events of AESI (hypersensitivity) will also be calculated.

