11.2 Inferential Methods

There will be no adjustment for multiple testing because there are only two treatment arms and a single primary endpoint. All other analyses (key secondary and other secondary endpoints) are considered as supportive to the primary endpoint.

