15.2 Secondary Endpoint Analyses

15.2.1 Key Secondary Endpoint Analyses

The key secondary endpoint is ACR20 at Week 12.

The ACR20 is a key efficacy measure for which a subject must have at least 20% improvement from baseline in the following ACR Core Set values:

• TJC (68 joint count) and

- SJC (66 joint count) and
- An improvement of at least 20% from baseline in at least three of the following five assessments:
 - Patient's Global Assessment of Disease Activity on a visual analog scale (VAS)
 - Patient's Assessment of Arthritis Pain
 - Patient's Assessment of Physical Function as measured by the HAQ-DI
 - Physician's Global Assessment of Disease Activity
 - Acute phase reactant as measured by CRP.

The proportion of subjects with an ACR20 response at Week 12 in the two treatment arms will be reported along with Exact 95% CIs, calculated with the Clopper-Pearson method. The 95% CI for the difference between treatment arms in the proportion of subjects with an ACR20 response at Week 12, calculated with the Newcombe method, will also be presented.

The analyses will be carried out on both the ITT and the PP analysis sets.

Proportions for the two treatment arms will also be presented broken down by the subgroups for the ITT analysis set as described in Section 10.2.6.

Missing data will be handled as described in Section 11.4.1.

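### The primary safety endpoint, any hypersensitivity AESI up to Week 52, has confidence intervals for each arm but none for the difference between arms

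*SAP*

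**What the plan says.** Protocol 4.1 sets a comparative aim: "The primary objective of this study is to evaluate the safety profile of MSB11022-CCI compared to Humira", up to Week 52. SAP 15.1 defines the primary endpoint as the occurrence of any treatment-emergent hypersensitivity AESI up to Week 52, analysed on the Safety Analysis Set.

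For that endpoint SAP 15.1 plans the proportion of subjects with an exact interval, "calculated with the Clopper-Pearson method) will be provided for each treatment arm". The one between-arm quantity is "Half width of 95% CIs for the difference between treatment arms in occurrence for the most commonly observed clinical events". The cut-off that selects those events is to be set before database lock and unblinding, and no interval method is named. Protocol 8.5.2 has the same plan: per-group incidence with 95% CIs, plus "Half width of 95% CIs for the difference in incidence for the most commonly observed clinical events of AESI". The synopsis agrees.

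Nothing elsewhere adds a between-arm interval. SAP 16.1.1 gives exposure-based incidence rates with exact Poisson intervals, by arm. SAP 16.2.3.1 refers back to 15.1.

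SAP 11.2 states: "All other analyses (key secondary and other secondary endpoints) are considered as supportive to the primary endpoint". Yet for the key secondary endpoint SAP 15.2.1 plans "The 95% CI for the difference between treatment arms in the proportion of subjects with an ACR20 response at Week 12", by the Newcombe method. ACR20 at other visits, ACR50 and ACR70 follow the same approach (SAP 15.2.2.1 and 15.2.2.2).

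**The concern.** The trial asks how MSB11022 compares with Humira on safety. As planned, the primary result will not itself state which differences in hypersensitivity are compatible with the data. A reader will see two per-arm intervals and must judge the comparison by eye.

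That can mislead in two ways. Two per-arm intervals can overlap when the interval for the difference excludes zero, so an imbalance may be missed. When the arms look alike, the per-arm intervals do not show how large a difference remains possible, and comparing their ends overstates it. The half-widths do not fill the gap. They concern component events, and on their own they give neither limits nor direction.

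The supportive efficacy endpoint therefore carries more between-arm information than the primary endpoint.

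**Working it through.** **Inputs.** Two-sided 95% intervals (SAP 11.1), so z = 1.96. Randomization is 1:1 with 130 per arm (Protocol 8.1); I assume all are dosed. The documents give no overall AESI rate for this population. Protocol 5.2.3.1 says "the rate of most commonly observed hypersensitivity events is 26.5% for the injection site reactions and 11% for rash", so I take about 26% as the main illustration and vary it. The low end comes from the healthy-volunteer study in Protocol 3.3, where hypersensitivity rates were 2.5% to 7.6%.

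**Formulas.** The Wilson limits for x/n, with p = x/n, are [p + z²/2n ± z√(p(1−p)/n + z²/4n²)] / (1 + z²/n). With d = p₁ − p₂ and Wilson limits (l, u) in each arm, the Newcombe interval is d − √[(p₁−l₁)² + (u₂−p₂)²] to d + √[(u₁−p₁)² + (p₂−l₂)²].

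**The plan's own precision figures.** Protocol 8.1 and SAP 7.1 give 12.0% at an incidence of 26.0% and 9.0% at 11.0%.

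| Half-width (points) | 26% | 11% |
|---|---|---|
| Difference, Newcombe, 100/arm | 12.06 | 8.99 |
| Difference, Wald, 100/arm | 12.16 | 8.67 |
| Single arm, Wald, n = 100 | 8.60 | 6.13 |
| Difference, Newcombe, 130/arm | 10.60 | 7.82 |
| Difference, Wald, 130/arm | 10.66 | 7.61 |

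The stated figures reproduce as half-widths for a between-arm difference at about 100 per arm. They do not reproduce as per-arm half-widths. The sizing therefore already thinks in terms of the difference, but only for two single event types. At these rates the unnamed method matters little.

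**Equal counts, 34 v 34 of 130 (26.2%).** The Clopper-Pearson interval in each arm is 18.8% to 34.6%. Subtracting opposite limits suggests ±(34.58 − 18.84) = ±15.7 points. The Wilson limits are 19.36% and 34.31%, so the Newcombe half-width is √[(26.15−19.36)² + (34.31−26.15)²] = √(6.79² + 8.16²) = 10.6 points.

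**Unequal counts, 52 v 34 of 130.**
- Clopper-Pearson: 40.0% (31.5 to 49.0) and 26.2% (18.8 to 34.6). These overlap.
- Wilson limits: 31.98% to 48.59%, and 19.36% to 34.31%.
- Difference: d = 13.85. Lower limit = 13.85 − √(8.02² + 8.16²) = 2.4. Upper limit = 13.85 + √(8.59² + 6.79²) = 24.8.

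**Range of counts.** The table shows which counts in the other arm give overlapping per-arm intervals although the Newcombe interval excludes zero (130 per arm).

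| Lower-arm count | Rate | Counts in the other arm | Newcombe half-width at equal counts |
|---|---|---|---|
| 3 | 2.3% | 11 to 14 | 4.5 |
| 10 | 7.7% | 21 to 26 | 6.8 |
| 26 | 20.0% | 40 to 47 | 9.7 |
| 34 | 26.2% | 49 to 56 | 10.6 |
| 46 | 35.4% | 62 to 69 | 11.5 |

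The pattern holds at every rate tried. The range of such counts narrows, and the interval shortens, at low rates.

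**The case against.** The strongest reply is that this is a presentation choice in a study declared descriptive. Protocol 5.2.1 says the trial cannot be powered for equivalence in safety, and it cites guidance that favours descriptive methods with confidence intervals where they help interpretation. Protocol and SAP agree with each other. No decision rests on whether an interval excludes zero. Any reader can compute the interval from the per-arm counts. Half-widths of difference intervals are planned for the common events, and with the event frequencies they nearly recover the limits: at 52 v 34, the point difference plus or minus the Newcombe half-width gives 2.6 to 25.0, against 2.4 to 24.8. The label supportive in SAP 11.2 explains the lack of multiplicity adjustment; it does not ration output. The output shells, which were not available, may already contain the row.

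Much of this stands, and it limits how serious the point is. It does not remove it. An interval for a difference is itself descriptive, the cited guidance allows it, and ACR20, also descriptive, has one. The half-widths do not cover the endpoint named as primary. Naming the method and direction before unblinding avoids a later choice, and SAP Section 5 requires analyses not planned there to be identified as such in the CSR. The 26% rate is an assumption, and the size of the interval depends on it.

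**Conclusion.** The concern holds. For the overall primary endpoint the plan contains no interval for the between-arm difference, although the objective is comparative. Between-arm precision is not wholly absent, since half-widths are planned for the most common component events, but these do not answer the primary question.

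With 130 treated per arm and equal observed counts, the missing interval would be about ±10.6 points if the overall rate is near 26%. Over the assumed range from 2.3% to 35.4% it would be about ±4.5 to ±11.5 points. The per-arm intervals do not convey this. It is a gap in presenting the primary estimate that should be fixed. It does not make the analysis invalid, and it affects no test, margin or decision.

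**What to change.** Add to SAP 15.1: *The difference between arms (MSB11022 minus Humira) in the proportion of subjects with any treatment-emergent hypersensitivity AESI up to Week 52, and with each of the most commonly observed events, will be presented with its 95% CI (Newcombe method, Safety Analysis Set).* The half-widths may stay alongside.

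The cost is one sentence, one table row for the overall endpoint and one interval per selected event, added before database lock and unblinding. The method is already in SAP 15.2.1. Protocol 8.5.1 leaves such detail to the SAP ("Full details of all planned analyses will be provided in the SAP, to be finalized and approved prior to database lock"), so the protocol text need not change. If the sponsor regards the interval as going beyond Protocol 8.5.2, a one-line entry in SAP Section 9 would record it. No extra patients, test or margin are needed.

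Optionally, and not as an error, the sponsor could confirm that the 12.0% and 9.0% precision refers to a between-arm difference at about 100 per arm.

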15.2 Secondary Endpoint Analyses

15.2.1 Key Secondary Endpoint Analyses

The key secondary endpoint is ACR20 at Week 12.

The ACR20 is a key efficacy measure for which a subject must have at least 20% improvement from baseline in the following ACR Core Set values:

• TJC (68 joint count) and

- SJC (66 joint count) and
- An improvement of at least 20% from baseline in at least three of the following five assessments:
 - Patient's Global Assessment of Disease Activity on a visual analog scale (VAS)
 - Patient's Assessment of Arthritis Pain
 - Patient's Assessment of Physical Function as measured by the HAQ-DI
 - Physician's Global Assessment of Disease Activity
 - Acute phase reactant as measured by CRP.

The proportion of subjects with an ACR20 response at Week 12 in the two treatment arms will be reported along with Exact 95% CIs, calculated with the Clopper-Pearson method. The 95% CI for the difference between treatment arms in the proportion of subjects with an ACR20 response at Week 12, calculated with the Newcombe method, will also be presented.

The analyses will be carried out on both the ITT and the PP analysis sets.

Proportions for the two treatment arms will also be presented broken down by the subgroups for the ITT analysis set as described in Section 10.2.6.

Missing data will be handled as described in Section 11.4.1.

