7.1 Sample Size

According to the European Medicine Agency (EMA) recommendation (EMA/CHMP/SAWP/200743/2016), a total of 100 patients/arm should be adequate for a study primarily focusing on safety. To account for drop outs, this descriptive study will include 260 randomized patients in total (130/arm) in order to ensure 200 subjects are in the study at Week 52. In fact, based on averaged originator's dropout rates at Week 52, a 20% rate of drop-out overall is included in the sample size calculation (1, 2, 3). This sample size will permit an informative assessment of the

occurrence of most common AESIs (> 1/10) such as injection site reactions and rash with a precision of 12.0% and 9.0% for the AESI incidence of 26.0% and 11.0% respectively (0).

A subset of 60 patients (30 per treatment arm) will be randomly selected across all sites to participate in population PK analysis.

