7.2 Randomization

Eligible subjects will be randomized in permuted blocks in a 1:1 ratio by an IWRS to receive either MSB11022-CCI sc or Humira sc at a dose of 40 mg every other week starting at baseline up to and including Week 48.

Randomization will be stratified by previous disease-modifying therapy use. Subjects will be stratified by the type of systemic therapy previously received: non-biological (biologic naïve subjects) versus biological (biologic experienced subjects). Subjects who previously received both (biological and non-biological systemic therapies) will be assigned to the "biological" group. The exposure to previous biological agents will be limited to one TNF inhibitor other than adalimumab. The participation of subjects in the previous biological systemic therapy stratum will be capped at 20% of the total number of subjects randomized.

8 Overview of Planned Analyses

Once the last subject has completed the 4-month safety follow-up visit, the database will be locked. The analysis will be performed using cleaned study data collected in electronic case report form (eCRF) or transferred from laboratories performing laboratory tests and biosample analysis until the date of the 4-month safety follow-up visit of the last subject. Once the data cleaning is complete, a data review meeting will be held prior to the database lock. In addition, no data can be frozen or locked and no randomization code should be unblinded until this Statistical Analysis Plan (SAP) has been approved.

The final analysis will include all data collected during the study up to week 52 date (or end of treatment date+28 days, whichever occurs later) for subjects who completed the study, and theoretical week 52 (ie 52 weeks after first intake) or 4 months safety follow-up visit, whichever occurs first, for subjects who early terminated the treatment.

All AE tables and listings will be re-produced to reflect any additional AEs and any updates to the reported AEs in final analysis. Additionally the concomitant medication and procedure tables and listings will be re-produced to reflect any updates.

In addition, an independent data monitoring committee (IDMC) will review safety and tolerability data of this study on an ongoing basis. The methodology and presentation of results for the IDMC are covered in the IDMC Charter and in Section 18.

9 Changes to the Planned Analyses in the Clinical Trial Protocol

Not applicable.

10 Protocol Deviations and Analysis Sets

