10.2.2 Intent-to-Treat Analysis Set

The Intent-To-Treat (ITT) Analysis Set includes all subjects randomly allocated to a treatment, based on the intention to treat "as randomized" principle (ie, the planned treatment regimen rather than the actual treatment given in case of any difference). Subjects will be analyzed according to their randomized treatment.

In the event that subjects are incorrectly stratified, ie subjects are randomized according to the incorrect stratification, these subjects will be analyzed under the randomized treatment but with the correct stratification value.

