11.1 Descriptive Methods

Descriptive statistics for continuous data will include the following:

- Number of subjects with non-missing data (n)
- Number of subjects with missing data
- Mean, standard deviation (SD)
- Median, first and third quartiles (Q1 and Q3)
- Minimum and maximum
- 95% confidence interval (CI).

All statistics will be rounded according to Merck's Global Biostatistics Output Standards (GBSOS) Booklet (Version 4.0 or later), ie, percentages will be rounded to one decimal. The mean, median, Q1, Q3, and 95% CI will be presented with one additional decimal compared to the raw data; SD will be presented with two additional decimals compared to the raw data; and minimum and maximum will be presented with the same number of decimals as the raw data.

All data will be presented by nominal visit (including the safety follow-up visits – four weeks and four months after the last dose of IMP) and no visit windowing rules will be implemented. Data from unscheduled visits will be listed but will not be included in summaries presented by

visit. The exceptions will be in the calculation of the baseline values. Data from unscheduled visits will also be included in the calculation of the worst on-treatment values and grades.

Categorical data will be summarized by presenting the number of subjects with non-missing data (n), the number of subjects with missing data (missing), and the number and percentage of subjects in each category. Percentages will be based on the number of subjects with non-missing data in the analysis set of interest, unless otherwise specified.

Time to event variables will be summarized by presenting Kaplan Meier estimates and 95% CIs.

Change from baseline will be calculated as the post-baseline value minus the baseline value. Percent change from baseline is defined as (100 x (post-baseline – baseline) / baseline).

If all baseline values are missing for a particular variable, the change from baseline and percent change/percent improvement from baseline will not be calculated.

A 2-sided significance level of 5% will be used for all analyses. Two-sided 95% confidence intervals will be calculated.

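### The between-arm ACR20 difference is given only as an unstratified Newcombe interval although randomisation is stratified by prior biologic use; a stratum-weighted difference should be added (minor)

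*SAP*

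**What the plan says.** On the design, SAP 7.2 states: "Randomization will be stratified by previous disease-modifying therapy use". There are two levels, biologic-naive and biologic-experienced, allocated 1:1 in permuted blocks. The experienced stratum "will be capped at 20% of the total number of subjects randomized".

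On the stratum value, SAP 10.2.2 says of ITT patients randomised under the wrong stratum that "these subjects will be analyzed under the randomized treatment but with the correct stratification value". SAP 10.2.3 excludes such patients from the PP set.

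On the analysis, SAP 15.2.1 gives Clopper-Pearson intervals per arm and, for the between-arm difference in Week 12 ACR20, an interval "calculated with the Newcombe method, will also be presented". It applies to ITT and PP. ACR20 at other weeks, ACR50 and ACR70 follow the same method (SAP 15.2.2.1 and 15.2.2.2).

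Stratum information appears in one place on the efficacy side. SAP 10.2.6 defines previous systemic therapy as a subgroup, and ACR20 and Week 12 ACR50 are shown by arm within it, for the ITT set only.

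The analysis is descriptive (protocol 5.2) and supportive to the primary safety endpoint (SAP 11.2). No margin, test or power is set for ACR20.

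**The concern.** When allocation is stratified, one expects the main between-arm estimate to use the stratum, or the plan to say why it does not. Here the SAP takes care to correct the stratum value and then gives it no role in any treatment comparison.

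Two things could follow. First, if response differs between strata, an interval that pools them counts between-stratum variation as error and is somewhat conservative. Second, stratified allocation balances the arms at randomisation, but not necessarily in the sets analysed:

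- Percentages use non-missing data by default (SAP 11.1), and non-responder imputation is described as a repeat of the ITT analysis (SAP 11.4.1), so the leading ITT result appears to be observed-case.
- The PP set drops patients who leave before Week 12, are under 80% compliant or lack the endpoint (SAP 10.2.3).

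Any stratum imbalance created this way stays in an unadjusted difference.

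**Working it through.** **Inputs from the documents.** 130 per arm; experienced stratum at most 20%, so at most 0.20 × 130 = 26 per arm; 1:1 allocation; two-sided 95%; 20% dropout at Week 52 (SAP 7.1, 7.2, 11.1).

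**Assumed, because the documents give no ACR20 rates.** 65% response in naive patients; experienced patients 10, 20 or 30 points lower; equal arms; the stratum filled to its cap.

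**1. The plan's own precision figure.** SAP 7.1 states 12.0% and 9.0% for AESI incidences of 26.0% and 11.0%. An unstratified Newcombe half-width for a difference of two equal proportions at 100 per arm gives 12.06 and 8.99 points, which matches. (Wald, 1.96 × √(2p(1−p)/100), gives 12.16 and 8.67.) The documents state no corresponding figure for ACR20.

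**2. Half-width for ACR20.** Pooled response is p = 0.8 × 0.65 + 0.2 × p_exp.

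- Unstratified Wald half-width: 1.96 × √(2p(1−p)/130).
- Mantel-Haenszel half-width: replace p(1−p) by the within-stratum variance, V = 0.8 × 0.65 × 0.35 + 0.2 × p_exp(1−p_exp).
- The two variances differ by 0.8 × 0.2 × gap².

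| Gap (points) | p | p(1−p) | V | V / p(1−p) | Wald, unstratified | Mantel-Haenszel | Narrowing |
|---|---|---|---|---|---|---|---|
| 10 | 0.63 | 0.2331 | 0.2315 | 0.993 | 11.74 | 11.70 | 0.04 |
| 20 | 0.61 | 0.2379 | 0.2315 | 0.973 | 11.86 | 11.70 | 0.16 |
| 30 | 0.59 | 0.2419 | 0.2275 | 0.940 | 11.96 | 11.60 | 0.36 |

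With no gap, both are 11.60 and nothing is gained. At 80% in naive and 50% in experienced patients, the Wald-type figures are 10.66 and 10.26.

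**3. The interval actually planned.** These are Newcombe half-widths in points. The stratified version puts Mantel-Haenszel-weighted Wilson limits into the Newcombe formula.

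| Gap (points) | Unstratified | Stratified |
|---|---|---|
| 10 | 11.59 | 11.59 |
| 20 | 11.70 | 11.70 |
| 30 | 11.80 | 11.80 |

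Across naive rates of 50% to 80% at 130 per arm, the two versions differ by at most 0.03 points, in either direction.

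**4. Coverage of the planned interval.** Simulation under stratified 1:1 allocation (400,000 runs per scenario) gives 95.0% with no gap, 95.2% with a 15-point gap, and 95.6% to 95.9% with a 30-point gap.

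**5. Imbalance after loss.** Suppose each arm starts with 26 of 130 experienced and n patients remain after random loss. The between-arm difference in experienced share then has SD = √(2 × 0.16/n × (130−n)/129). The resulting SD in the ACR20 difference is that share SD times the gap.

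| Loss | n | SD of share difference | Gap 10 | Gap 20 | Gap 30 |
|---|---|---|---|---|---|
| 10% | 117 | 1.66 points | 0.17 | 0.33 | 0.50 |
| 20% | 104 | 2.49 points | 0.25 | 0.50 | 0.75 |

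The 20% row borrows the Week 52 dropout rate, so it is likely to be high for Week 12. Loss related to treatment or response could produce more. A stratum-weighted difference largely removes this component.

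**The case against.** The case against acting is substantial. ACR20 is descriptive, with no margin or test, so a few tenths of a point on a half-width of about 11.7 change no decision. The planned interval holds its nominal coverage. ITT proportions by stratum are already planned, so the corrected stratum value has some use. All of this stands, and it keeps the point minor.

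Four stronger readings are tempting, and the documents do not support them:

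- *The interval is materially too wide.* The narrowing in step 2 is between two Wald-type intervals, and Wald is not the planned method. Against the planned method, the stratified Newcombe form in step 3 gains nothing. A different construction, combining squared distances to the stratified Wilson limits, gives 11.48, 11.48 and 11.39 points, so even the sign of a gain depends on which stratified form is meant.
- *Prior biologic use was made a stratum because it predicts response.* Neither document gives a reason for stratifying. The protocol refers to other trials only in support of the 20% cap.
- *The SAP ignores the design.* The ITT subgroup table shows otherwise. What is missing is a difference combined across strata, and any stratum information in the PP set.
- *Every binary endpoint should be stratified.* The experienced stratum has at most about 26 patients per arm. At the 11% rash incidence, that is 26 × 0.11, or about 3 events per arm, and SAP 10.2.6 itself expects too few data for ACR70 subgroups.

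What remains after these concessions is the adjustment for imbalance in the observed-case and PP analyses, and the corrected stratum value that no comparison uses.

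**Conclusion.** The point holds as a minor one. The between-arm ACR20 difference does not use the randomisation stratum, and the corrected stratum value in SAP 10.2.2 enters no between-arm comparison. The planned interval is nonetheless valid: simulated coverage is 95.0% to 95.9%.

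Precision is not the reason to change. The gain is 0.04 to 0.36 points on a Wald-type half-width, and none with the stratified Newcombe form. The reason is a point estimate adjusted for stratum imbalance, worth about 0.2 to 0.75 points (one SD) under random loss of 10% to 20%. It does not apply to the non-responder-imputed ITT analysis to the same degree, since that analysis keeps all randomised patients.

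These sizes rest on assumed response rates and gaps and on a stratum filled to its cap. If the strata respond alike, there is no gain; if the stratum is smaller, the gain is smaller.

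**What to change.** In SAP 15.2.1, and for Week 12 ACR50 in SAP 15.2.2.2, add for both ITT and PP the Mantel-Haenszel stratum-weighted risk difference with a 95% CI based on the stratified (Mantel-Haenszel) variance, using actual prior-biologic status. Name the variance explicitly, because the alternatives behave differently. Keep the unstratified Newcombe interval alongside. This also gives the corrected stratum value in SAP 10.2.2 a defined purpose.

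Do not require it for ACR70 or the AESI difference, where the biologic stratum may be too sparse.

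The cost is one or two sentences in the SAP and an extra line in existing tables, using standard software. It should be settled before unblinding.
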